***PART 2 (Independently at home by Subject):***

- Shortly after the conclusion of Baseline, Part 1, and on the same day, subjects will receive access to complete a video-guided VR onboarding session providing information to set-up the VR headset and information about the intervention.
- Subjects will be able to reach out to a designated, unblinded site support team for any assistance/guidance during the video-guided onboarding session or at any time thereafter.
- After successful video onboarding, subjects will complete the first VR session.

- Then, after completion of the first VR session, subjects complete the CEQ electronically.

The designated, unblinded site support team will ensure that the video-onboarding, the first VR session, and the CEQ are completed all *within the same day as Baseline, Part 1*.

- During the rest of Week 1 (days 2-7), subjects will be expected to continue their engagement with the VR intervention and to complete a minimum of two additional VR sessions for a weekly total of three completed VR sessions.
- Subjects are also encouraged to engage with the optional VR content.

#### **11.5.4. Intervention period (Weeks 2, 4, 6, and 8/EOS)**

These intervention weeks will be split into multiple parts: Part 1, independent at-home activities completed by the subjects, Part 2, a telehealth visit with investigator site staff, and for Week 8/EOS ONLY, an additional Part 3, where after the telehealth call, a qualitative interview with a member of the unblinded site support team will take place. The details are further outlined below:

##### ***PART 1 (Independently at home by Subject):***

- Minimum of 3 required VR sessions (Must be completed prior to PROs).
- Subject electronically completes PHQ-9.
- Subject electronically completes PGI-I.
- Subject electronically completes CEQ (Week 6 and Week 8 ONLY).
- Subjects are encouraged to engage with optional content and to review content completed at any time.
- In the event that subjects require technical support or further VR program instructions, support will be provided by a designated unblinded site support team (ie, personnel external to the site and not involved in data collection).

The scales should be reviewed upon their completion on a bi-weekly basis, to ensure completeness, for any potential AEs that may be reported, and retraining provided to subjects as necessary. Weekly reminders to all study subjects to complete their modules and PROs will be sent out. Subjects that fail to complete weekly content requirements will be contacted directly by the unblinded site support team, who will closely monitor intervention compliance for both groups.

##### ***PART 2 (investigator site staff during telehealth Visit 4 (W2)/ Visit 5 (W4) / Visit 6 (W6)/ Visit 7 (W8/EOS)):***

During the last 3 days of Weeks 2, 4, 6, and 8, the investigator site staff will conduct telehealth study visits to complete the following assessments:

- Clinician administers C-SSRS. (Week 4 and Week 8 ONLY)
- Clinician administers LSAS.
- Clinician completes CGI-S.
- Clinician completes CGI-I.

- Collect AEs and concomitant medication changes.

All attempts will be made to ensure that each subject is assessed by the same study staff to minimize confounding bias due to changing assessors.

Unscheduled telehealth visits to complete/perform additional safety assessments, may be conducted as deemed necessary by the investigator site staff/subject.

After the completion of the telehealth portion of visit 7 with investigator site staff, the second part of the visit will be conducted separately by a member of the unblinded site support team where the Qualitative Interview will be completed as the final study assessment on the same day or within no later than 48 hours. During this visit, the unblinded site support team will instruct the patient to return the device and provide any necessary guidance/instructions.

#### **11.5.5. Intervention Period (Weeks 3, 5, and 7)**

Independently at home by subject:

- Minimum of 3 required VR sessions.
- Subjects are encouraged to engage with optional content and to review content completed at any time.
- In the event that subjects require technical support or further VR program instructions, support will be provided by a designated unblinded site support team (ie, personnel external to the site and not involved in data collection).

There are no telehealth visits scheduled during these weeks; however, unscheduled telehealth visits to complete/perform additional safety assessments, may be conducted as deemed necessary by the investigator site staff/subject.

#### **11.5.6. Early Termination**

For subjects who prematurely discontinue from the study, every effort should be made to complete the final evaluation procedures, as described in [Section 11.5.4](#) and including clinical and PRO assessments , as well as the Qualitative Interview outlined in [Section 11.3.7](#) at the ET visit. This ET visit should occur within 5 days of the last exposure to the Investigational Intervention, including the qualitative interview and PROs if they have not been completed by the subject for the given week.

## 12. SAFETY REPORTING

### 12.1. Definitions

#### 12.1.1. Adverse Events

An adverse event (AE) is any untoward medical occurrence associated with the use of an investigational intervention in humans, whether or not considered related to the intervention.

Untoward medical occurrences that occur after the time of signing the Informed Consent Form (ICF) and prior to the first VR session are a subset of AEs referred to in analysis as pre-treatment events. Those that occur after first VR session are considered AEs. Importantly, all AEs, including pre-treatment events, are collected via the same form by investigator site staff, who will complete the AE form in the EDC, which will then immediately notify both the CRO and Sponsor.

An AE can, therefore, be any unfavorable and unintended sign (including an abnormal laboratory finding), symptom, or disease occurring after the administration of an investigational intervention, whether or not considered related to the investigational intervention. AEs may include the onset of new illness and the exacerbation of pre-existing conditions. AEs will be collected from after first use of the investigational intervention to the EOS/ET.

The Investigator should attempt to establish a diagnosis of the event based on signs, symptoms, and/or other clinical information. In such cases, the diagnosis should be documented as the AE and not the individual signs/symptoms.

#### 12.1.2. Serious Adverse Events

A serious adverse event (SAE) is an AE that meets one or more of the following criteria:

- Results in death.
- Is life-threatening.
- Requires hospitalization or prolongation of existing hospitalization.
- Results in persistent or significant disability or incapacity.
- Is a congenital anomaly or birth defect.
- Is an important medical event that may jeopardize the subject or may require a medical or surgical intervention to prevent one of the outcomes listed above.  
Examples of such medical events include allergic bronchospasm requiring intensive treatment in an emergency room or at home, blood dyscrasias or convulsions that do not result in inpatient hospitalization.

The term "severe" is often used to describe the severity of a specific event (as in mild, moderate, or severe myocardial infarction) (see [Section 12.2](#)); the event itself, however, may be of relatively minor medical significance (such as severe headache). This is not the same as "serious," which is based on subject/event outcome or action criteria usually associated with events that pose a threat to a subject's life or functioning as defined by the criteria above.

During the study, if a subject has a hospitalization or procedure (eg, elective surgery) that was scheduled before the study entry, ie, before informed consent for an event/condition that occurred before the study, the hospitalization is considered a therapeutic intervention and not the result of a SAE. However, if the event/condition worsens during the study, it should be reported as an AE (or SAE, if the event/condition results in a serious outcome such as prolongation of hospitalization).

Life-threatening means that the subject was, in the view of the Investigator, at immediate risk of death from the event as it occurred. This definition does not include an event that had it occurred in a more severe form might have caused death.

SAE criteria information will be captured on the CRF.

### **12.1.3. Unanticipated Adverse Device Effects**

An unanticipated adverse device effect (UADE) is any serious adverse effect on health or safety, any life-threatening problem or death caused by, or associated with a device, if that effect, problem, or death was not previously identified in nature, severity, or degree of incidence in the application; or any other unanticipated serious problem associated with a device that relates to the rights, safety, or welfare of subjects.

## **12.2. Collection and Recording of Adverse Events**

All pre-treatment events and AEs including UADEs must be recorded in the subject's study records/source documents in accordance with the Investigator's normal clinical practice. All pre-treatment events and AEs must be recorded on the CRF.

All AEs will be followed until resolution, stabilization of the condition, the event is otherwise explained, the completion of the study, or the subject is lost to follow-up.

Each AE is to be evaluated for duration, severity, frequency, seriousness, action taken with the investigational intervention, outcome, and causal relationship to the investigational intervention. Definitions for severity, frequency, action taken with the investigational intervention, outcome, and causal relationship to the investigational intervention are presented below.

The severity of AE:

- **Mild** - Ordinarily transient symptoms that do not influence performance of subject's daily activities. Other treatment is not ordinarily indicated.
- **Moderate** - Marked symptoms sufficient to make the subject uncomfortable. Moderate influence on performance of subject's daily activities. Other treatment may be necessary.
- **Severe** - Symptoms cause considerable discomfort. Substantial influence on subject's daily activities. May be unable to continue the study, and other treatment may be necessary.

The frequency of AE:

- **Once** – an isolated episode.
- **Intermittent** – occurs on two or more separate occasions.

- **Continuous** – does not abate from date of onset to date of resolution.

The action taken with the investigational intervention:

- **None**
- **Removed temporarily**
- **Removed permanently**
- **Replaced**
- **Action taken with component(s)**
- **Unknown**

The outcome of the AE:

- **Recovered/Resolved**
- **Recovering/Resolving**
- **Not Recovered/Not Resolved**
- **Recovered/Resolved with Sequelae**
- **Fatal**
- **Unknown**

The causal relationship of the AE to the investigational intervention:

- **Not related:** - Improbable temporal relationship and is plausibly related to other drugs/products or underlying disease.
- **Related**
  - **Possible** - occurred in a reasonable time after the use of the intervention, but could be related to concurrent drugs or underlying disease.
  - **Probable** - occurred in a reasonable time after use, is unlikely to be attributable to concurrent drugs or underlying disease, and there is a plausible mechanism to implicate the intervention.
  - **Definite** - occurred in a reasonable time after use and cannot be explained by concurrent drugs or underlying disease. The adverse event should respond to dechallenge/rechallenge, however, this is not mandatory before assigning a definite causality.

The Medical Monitor is the initial contact person for protocol related questions or discussion of AEs. The contact information for the Medical Monitor as well as other emergency contact information can be found in [Table 1](#) of this protocol.

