### **7.2.2. Blinding**

Subjects, Investigators, investigator site staff, persons performing the assessments, clinical operations personnel, data analysts, will remain blinded to the identity of the VR intervention from the time of randomization until database lock and unblinding, using the following methods:

- Randomization data are kept strictly confidential until the time of unblinding in the IWRS, and will not be accessible by anyone else involved in the study with the

following exceptions: Unblinded site support team to support the subjects with any technical VR device issues and performing qualitative interview, pharmacovigilance department for evaluation and reporting of UADEs, SAEs, and any other AEs of clinical interest.

- The identity of the interventions will be concealed by the use of VR headsets that are all identical in packaging, labeling, schedule of administration and appearance.

In order to secure subject blinding, subjects will have no prior experience with CBT. Subjects will be instructed and reminded on an ongoing basis not to share descriptions of the intervention they are receiving in any capacity with investigator site staff (with the exception of the unblinded site support team) during visits or at any point during study participation and discouraged from discussing details of the therapy outside the study.

Investigator site staff will not be provided the details of the study intervention and various components/experiences within the program beyond the broad overview that is presented in this protocol to minimize any chance of unblinding. The VR device allocated to each subject upon randomization will be shipped directly to the subject's address from the depot and any activities, including subject training/tech support related to the VR intervention will be managed by the unblinded site support team external to the site, removing the investigator site staff from the entire process to minimize any chance of unblinding.

Actual subject identity revealing actual study treatment will not be disclosed before database lock and study unblinding unless an emergency unblinding becomes necessary.

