#### **15.4.3.1. Adverse Events**

All AEs will be coded using MedDRA version 26.0 or higher. AEs are untoward medical occurrences:

- that occurred on or after the first BVR-100/BES-100 use,
- with a missing start date and a stop date on or after the first BVR-100/BES-100 use, or
- with both a missing start and stop date.

AEs will be summarized by MedDRA SOC and PT.

The following AEs will be summarized and presented by MedDRA SOC and PT for the Safety population:

- All AEs (including number of events and subject incidence).
- AEs by severity (mild, moderate, severe).
- AEs by relationship to the investigational intervention (related, or not related).

The following conventions will be followed in summarizing AEs:

- For subject incidence summaries, each subject will be counted only once within each SOC and within each preferred term.
- If a subject reports more than one AE within a preferred term and/or a body system, the AE with the highest known severity within each body system and within each preferred term will be included in the summaries by severity.
- For summaries by relationship to the investigational intervention, AEs will be grouped as “related” or “not related.” AEs assessed as “possible,” “probable,” or “definite,” will be grouped as “related.” If a subject reports more than one AE within, SOC and PT, and any are related, it will be summarized as related. AEs whose relationship to the investigational intervention is assessed as “not related” or “unlikely” will be grouped as “not related.”

A listing of AEs, as well as a listing of deaths, SAEs, UADEs, or AEs leading to discontinuation, will be presented.

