11.15 Adverse Events

Any Adverse Event (AE) is defined as any effect that occurs or worsens after the first VR session until EOS will be summarized. Any events that occur after the time of signing the Informed Consent Form (ICF) and prior to the first VR session are termed as pre-treatment events.

Related Adverse Events include Possibly, Probably and Definitely Related Adverse Events.

UADEs are serious adverse effects caused by, or associated with a device which were not previously anticipated to occur. UADEs collected in CRF data will be summarized.

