12.10.4 Summary of Adverse Events by Relationship and Severity

Number and percentage of subjects in each system organ class, preferred term will be summarized by relationship and severity for adverse events and treatment group. System organ class and preferred term will be displayed by descending order of frequency in “Total”. Total will not be displayed in the table.

For summaries of relationship,

- AEs will be grouped as “related” or “not related.” AEs assessed as “possible,” “probable,” or “definite,” will be grouped as “related.”
- If a subject had multiple occurrences of the same preferred term within a system organ class, then it is counted once with closest relationship under the preferred term within the system organ class.
- If a subject had different preferred terms within the system organ class with different relationship, it is counted once within closest relationship within the system organ class and “Any AE” categories.

For summaries of severity,

- If a subject has multiple occurrences of the same preferred term within a system organ class, then it is counted once with maximum severity under the preferred term within the system organ class.
- If a subject had different preferred terms within the system organ class with different grades of severity, it is counted once within maximum severity grade within the system organ class and “Any AE” categories.

Above analysis details are specified in DDP: Table 14.3.1.8, Table 14.3.1.9

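### Protocol 12.2 requires both improbable timing and another drug or disease cause for *Not related*, so some coincidental AEs fit only *Possible*, others fit no grade, and 12.3.2 and 15.4.3.1 disagree with it

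*Protocol*

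**What the plan says.** Protocol 12.2 gives four causality grades.

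- *Not related*: "Improbable temporal relationship and is plausibly related to other drugs/products or underlying disease".
- *Possible*: "occurred in a reasonable time after the use of the intervention, but could be related to concurrent drugs or underlying disease".
- For *Probable*, the timing must again be reasonable, another drug or the underlying condition must be an unconvincing explanation, and a mechanism must be conceivable.
- *Definite*: "occurred in a reasonable time after use and cannot be explained by concurrent drugs or underlying disease".

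The last three sit under the heading *Related*. All three need the event to follow use within a reasonable time, and neither document says how long that is.

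Three other places deal with relationship:

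- Protocol 12.3.2, on unanticipated adverse device effects, counts adverse events caused solely by the underlying disorder or by circumstances outside the trial as unrelated to participation. It sets no timing condition.
- Protocol 15.4.3.1 pools the grades for analysis: "AEs whose relationship to the investigational intervention is assessed as “not related” or “unlikely” will be grouped as “not related". No *unlikely* grade appears in 12.2.
- The SAP pools the three upper grades in 11.15 ("Related Adverse Events include Possibly, Probably and Definitely Related Adverse Events") and in 12.10.4 ("AEs assessed as “possible,” “probable,” or “definite,” will be grouped as “related"). It does not mention *unlikely*.

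**The concern.** *Not related* is defined by two conditions joined by *and*, while *Possible* is open to any well-timed event even when something else could explain it. Read literally, a well-timed illness with an obvious other origin has to be called related, and some events cannot be graded at all. The protocol offers a way out in 12.3.2 and assumes another in 15.4.3.1, but neither matches the definitions that investigators are given for recording AEs. Two investigators could grade the same event differently, and each could cite the protocol.

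The grades feed planned outputs. SAP 12.10.2 to 12.10.4 specify summaries of related AEs, related serious AEs and AEs by relationship. Under 12.10.4 a subject is counted at the closest relationship within a system organ class and under any AE, so one *Possible* event is enough to move a subject into the related row.

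**Working it through.** The plan states no figure for this point. The check has two parts: whether the grades cover every case, and how many coincidental events a literal reading would affect.

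**1. Coverage of the grades.** Cross the two features used in 12.2: timing, and whether another drug, product or underlying disease could account for the event.

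| Timing | Other drug/disease cause | Grade that fits under 12.2 | Pooled as |
|---|---|---|---|
| Reasonable | Yes | *Possible* only | Related |
| Reasonable | No | *Probable* or *Definite* | Related |
| Improbable | Yes | *Not related* | Not related |
| Improbable | No | None | Undefined |

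Only one of the four cells leads to *Not related*. The first row is the misclassification: a clear other cause does not help if the timing is reasonable. The last row is a gap: an accidental injury remote from any session is neither a drug effect nor underlying disease, so it meets no definition.

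**2. Comparison with the other sections.** Under 12.3.2, an event in the first or last row that is solely due to something else is unrelated. Under 12.2 the same event is related or ungraded. The two sections therefore give different answers for the same facts. Under 15.4.3.1, a first-row event could have been placed in *unlikely* and pooled with *not related*, but 12.2 does not offer that grade.

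**3. Size.** Inputs:

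- At least three required sessions a week in both groups (Protocol 7.1). Over 8 weeks this is 3 × 8 = 24 active days at one session a day, which agrees with SAP 11.17.5.
- A week of 7 × 24 = 168 hours.
- Length of the reasonable-time window, *w*: not given, so assumed here to lie between 6 and 72 hours.
- Coincidental onsets assumed to fall at random through the week, with sessions on three separate days at the same hour.

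Share of onsets inside the window = hours of the week lying within *w* hours after a session ÷ 168.

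- For *w* up to 24 h the windows do not overlap, so the share is 3*w*/168. At 6 h: 18/168 = 11%. At 12 h: 36/168 = 21%. At 24 h: 72/168 = 43%.
- At 48 h with sessions on three consecutive days: (48 + 48)/168 = 96/168 = 57%. On alternate days: 3 × 48/168 = 144/168 = 86%.
- At 72 h on consecutive days: (48 + 72)/168 = 120/168 = 71%. On alternate days: (96 + 72)/168 = 168/168 = 100%.

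The share of coincidental onsets that a literal reading would grade as related thus runs from about 11% to 100%, and the deciding quantity is one the protocol does not set.

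**The case against.** The strongest reply is that investigators keep enough discretion to grade sensibly. Reasonable time is left to them, and Protocol 4.4 expects VR effects to be transitory, which favours a short window. An illness that starts well away from a session can then be called improbable in timing and graded *Not related*. Protocol 12.3.2 gives a written route to unrelated for events with a clear outside cause. The SAP takes precedence over the protocol's statistical section and does not use *unlikely*, so that category may simply stay empty. Safety is descriptive, both arms share the scale and the minimum schedule, and all AEs are also tabulated by system organ class and preferred term and listed in full.

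Much of this stands, and it limits the point. A reader might infer that three sessions a week force nearly every coincidental AE into related. The documents do not support that: it needs a window of about two days or more, which they nowhere state. A reader might also infer that staff who are not told the intervention's content cannot judge mechanism. They do have the protocol's overview and the risks listed in 4.4, and moving an event between *Probable* and *Possible* would not change the pooled count.

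The reply does not remove the defect. SAP precedence covers the protocol's statistical section, not 12.2, so the 12.2 definitions still govern how AEs are recorded. The route in 12.3.2 sits in another section and contradicts 12.2 rather than qualifying it. The AE form is not among the documents, so it cannot be assumed to resolve the mismatch.

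**Conclusion.** The point holds as a fault in the written definitions. *Not related* is too narrow, one combination of timing and cause has no grade, and 12.2, 12.3.2 and 15.4.3.1 do not agree. The consequence is related counts that are inflated and that vary between investigators, in both arms. The extent depends on the undefined window: about 11% to 100% of randomly timed onsets for assumed windows of 6 to 72 hours. That range rests on random onset times and three sessions a week on separate days; additional optional sessions on other days would raise the shares at a given window.

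No between-arm bias is evident, since scale, minimum schedule and blinded raters are common to both groups. It would also go too far to infer that the safety findings taken into the later trial would be wrong. Totals by term and arm are unaffected; what loses specificity is the related label, in the direction of over-attribution.

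**What to change.** - In Protocol 12.2, let *Not related* apply when the temporal relationship is improbable **or** the event is clearly explained by another drug, product, disease or circumstance. This closes the gap and agrees with 12.3.2.
- Settle *unlikely* in one of two ways. Either define it in 12.2, offer it on the AE form if it is not already there, and state in SAP 11.15 and 12.10.4 that it is grouped with *not related*; or delete it from Protocol 15.4.3.1.

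The cost is a wording change in the protocol, in the SAP too if *unlikely* is kept, and possibly one option on the AE form. The main burden is that investigators must re-confirm the relationship of AEs already entered. SAP section 13 reports 52 subjects in the Safety Population at the January 2024 data cutoff, so this is a bounded task, but it has to be done while raters are still blinded and before database lock.
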